### 2. SUMMARY/SYNOPSIS

Short title	ISOS study				
Methods	International, 7-day observational cohort study of complications following elective surgery				
Research sites	Hospitals undertaking elective surgery worldwide				
Objective	To provide detailed data describing post-operative complications and associated mortality				
Number of patients	Not specified. All eligible patients undergoing surgery during the study week.				
Inclusion Criteria	All adult patients (aged ≥18 years) undergoing elective surgery during the 7 day study period with a planned overnight stay				
Statistical analysis	Univariate analysis will be used to test factors associated with surgical complications, admission to critical care and in-hospital death. Single and multi-level logistic regression models will be constructed to identify factors independently associated with these outcomes and to adjust for differences in confounding factors. A stepwise approach will be used to enter new terms. A single final analysis is planned at the end of the study.				
Proposed Start Date	A seven day period between April and June 2014				
Proposed End Date	Data collection will end by August 2014				
Study Duration	Four months				

ISOS protocol v1.0 Page 4 of 16

#### 3. INTRODUCTION

Over 230 million patients undergo surgery worldwide each year with reported hospital mortality between 1 and 4%. 1-3 Complications following major surgery are a leading cause of morbidity and mortality. 4-9 In the overall population, the incidence of postoperative complications and death is low. However, studies suggest the existence of a high-risk sub-group of surgical patients which accounts for 80% of post-operative deaths but less than 15% of in-patient procedures. Patients who develop complications but survive to leave hospital often suffer reductions in functional independence and long-term survival. 4-6 In the Whitehall II study, British civil servants who took sickness absence from work were followed up for long-term survival. Sickness absence to undergo surgery was second only to cardiovascular disease in terms of associated long-term mortality.4 Data from the National Surgical Quality Improvement Programme in the USA suggests that survival amongst patients who develop post-operative complications varies between hospitals, suggesting both the potential and need to improve clinical outcomes in this population. 10 With the high volumes of surgery performed, even a low rate of avoidable harm will be associated with a large number of preventable deaths. There is increasing recognition of the massive potential impact of even small improvements in peri-operative care. 11

A recent study provided the first report of post-operative outcomes at a European level (EuSOS). The findings of this study suggest that post-operative mortality may be higher than previously thought and that mortality may vary between nations, again suggesting preventable deaths may occur. However, the EuSOS dataset did not include complications following surgery. The study group made a pragmatic decision to focus on the most readily collectable data with detailed follow-up of those patients admitted to the critical care unit. EuSOS was also confined to nations in geographical Europe. As a result, our understanding of peri-operative outcomes at an international level is incomplete and the need remains for data describing the frequency, severity and nature of complications following surgery and the associated short-term mortality. Our aim is to conduct an international seven-day cohort study of adults undergoing in-patient elective surgery to provide detailed data describing post-operative complications and associated mortality.

ISOS protocol v1.0 Page 5 of 16

#### Primary objective

To confirm the incidence of 30-day in-hospital complications following elective inpatient surgery.

#### Secondary objectives

- 1. To confirm the 30-day in-hospital mortality associated with these complications
- 2. To describe the relationship between critical care admission and postoperative complications
- 3. To describe the effect of post-operative complications on duration of hospital stay

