#### 7. STATISTICAL ANALYSIS

#### Sample size calculation

Our plan is to recruit as many centres as possible on an international basis and ask them to include all eligible patients in the study. A minimum of ten centres from any country will be required for participation and only centres including 20 valid patients will be included in the data analysis. We do not have a specific sample size and statistical models will be adapted to the event rate provided by the sample recruited.

ISOS protocol v1.0 Page 8 of 16

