#### Statistical analysis

Hospitals including data describing less than 20 valid patients will be excluded in the data analysis. Data will be presented in the following geographical regions: Australasia, North America, Central & South America, Western Europe, Eastern Europe, Northern Europe, Southern Europe, Indian sub-continent, Middle East, China & South-East Asia, North Africa, Sub-Saharan Africa and Central Asia. No comparison will be made between individual nations and all national and institutional level data will be anonymised prior to publication. Categorical variables will be described as proportions and will be compared using chi-square or Fisher's exact test. Continuous variables will be described as mean and standard deviation, if normally distributed, or median and inter-quartile range, if not normally distributed. Comparisons of continuous variables will be performed using one-way ANOVA or Mann-Whitney test as appropriate. Univariate analysis will be performed to test factors associated with post-operative complications, admission to critical care and in-hospital death. Single-level and hierarchical multi-level logistic regression models will be constructed to identify factors independently associated with these outcomes and to adjust for differences in confounding factors. Factors will be entered into the models based on their univariate relation to outcome (p<0.05), biological plausibility and low rate of missing data. A stepwise approach will be used to enter new terms. Results of logistic regression will be reported as adjusted odds ratios (OR) with 95% confidence intervals. The models will be assessed through the use of sensitivity analyses to explore possible interacting factors and examine any effect on the results. A single final analysis is planned at the end of the study.

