#### Primary outcome measure

In-hospital post-operative complications of any cause (censored at 30 days following surgery).

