#### Secondary outcome measures

- In-hospital all-cause mortality (censored at 30 days following surgery)
- Admission to critical care (within 30 days following surgery)
- Duration of hospital stay (duration of primary hospital stay after surgery)

ISOS protocol v1.0 Page 9 of 16

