## Post-operative Follow Up

Infection							
Wound infection	Mild 🗌	Moderate 🗌	Severe	None 🗌			
Body cavity	Mild 🗌	Moderate 🗌	Severe	None 🗌			
Pneumonia	Mild 🗌	Moderate	Severe	None 🗌			
Urinary tract	Mild 🗌	Moderate 🗌	Severe	None 🗌			
Bloodstream	Mild 🗌	Moderate	Severe	None 🗌			
Cardiovascular							
Myocardial infarction	Mild 🗌	Moderate	Severe	None 🗌			
Arrhythmia	Mild 🗌	Moderate	Severe	None 🗌			
Pulmonary oedema	Mild 🗌	Moderate 🗌	Severe	None 🗌			
Pulmonary embolism	Mild 🗌	Moderate 🗌	Severe	None 🗌			
Cardiac arrest	Mild 🗌	Moderate 🗌	Severe	None 🗌			
Stroke	Mild 🗌	Moderate 🗌	Severe 🗌	None 🗌			
Other							
Gastro-intestinal bleed	Mild 🗌	Moderate 🗌	Severe	None 🗌			
Other post-operative bleed	Mild 🗌	Moderate	Severe	None 🗌			
Acute kidney injury	Mild 🗌	Moderate 🗌	Severe 🗌	None 🗌			
Delirium	Mild 🗌	Moderate 🗌	Severe	None 🗌			
ARDS	Mild 🗌	Moderate 🗌	Severe 🗌	None 🗌			
Anastomotic leak	Mild 🗌	Moderate 🗌	Severe	None 🗌			
Medical error	Mild 🗌	Moderate 🗌	Severe	None 🗌			
Other	Mild 🗌	Moderate 🗌	Severe	None 🗌			
Critical care admission any time during hospital stay? ☐ Y ☐ N							
If yes, day of critical care admission (day 0=day of surgery):							
If yes, duration of critical care stay (days):							
-	, ,	-					
Duration of hospital stay after surgery (days):							
Survival at 30 days after su	☐ Alive	□ Dead					

ISOS protocol v1.0 Page 16 of 16

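### Objective 3 asks for the effect of complications on stay, but a complication counts only before discharge and its day is not recorded, so stay before onset cannot be separated from stay after it

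*Protocol*

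**What the plan says.** - **Objective** (Protocol, Secondary objectives, item 3): "To describe the effect of post-operative complications on duration of hospital stay".
- **Exposure** (Protocol section 7, Primary outcome measure): "In-hospital post-operative complications of any cause (censored at 30 days following surgery"). Time at risk therefore ends at discharge or day 30, whichever comes first.
- **Outcome** (Protocol section 7, Secondary outcome measures): "Duration of hospital stay (duration of primary hospital stay after surgery"). The clock starts at surgery, not at the complication.
- **Method** (Protocol section 7, Statistical analysis): "Comparisons of continuous variables will be performed using one-way ANOVA or Mann-Whitney test as appropriate". The modelling text covers other outcomes: "Univariate analysis will be performed to test factors associated with post-operative complications, admission to critical care and in-hospital death". The logistic models that follow address those same three outcomes, so no model for stay is described.
- **Data** (Protocol appendix, Post-operative Follow Up): each complication is graded mild, moderate, severe or none, with no day or date. Stay is one total, "Duration of hospital stay after surgery (days"). Among the in-hospital events on this page, only critical care admission has a day: "If yes, day of critical care admission (day 0=day of surgery").

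**The concern.** Whether a patient belongs to the complicated group depends on how long that patient stayed. Someone who leaves on day 2 cannot have a day-5 complication counted; someone kept for an unrelated reason can. Comparing total stay between patients ever and never complicated treats the complication as if it were known on day 0. Days spent in hospital before onset are credited to it, and longer stayers are selected into the exposed group. This is time-dependent bias, and adjustment for baseline case mix does not remove it.

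At stake is the answer to one secondary objective. Part of any reported difference in stay would be produced by the definitions and would be present even if complications prolonged nobody's stay. The form holds no onset day, so the core dataset would not allow this part to be separated out afterwards.

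**Working it through.** **Plan's own figure.** There is none to reproduce. The protocol gives no expected stay, complication rate, onset pattern or effect for this objective, and on size it says "We do not have a specific sample size and statistical models will be adapted to the event rate provided by the sample recruited". Every input below is an assumption, so ranges are shown.

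**Set-up.** Draw stay T and latent complication time C independently, so the true effect is zero. Count a complication when C < min(T, 30 days). Compare T between patients with and without one.

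**Analytic check.** Let T be exponential with discharge rate d and C exponential with rate c, ignoring the 30-day cap.
- Without a complication: E[T | T < C] = 1/(c + d).
- With one: E[T | C < T] = 1/(c + d) + 1/d.
- Difference: 1/d, the mean stay itself, although the effect is zero.

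At a mean stay of 4 days this predicts 4 days. Simulation with the cap gave 3.96 to 4.01 days for complication rates of 5% to 20%.

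**Log-normal stay, no true effect.** The ranges examined were median 3 to 4 days and log-SD 0.6 to 0.8, with either a constant hazard of 0.03 to 0.04 per day or gamma onset with mean 2 to 4 days in 20% to 30% of patients.

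| Median stay, log-SD | Onset | Incidence | Spurious difference in medians |
|---|---|---|---|
| 4 days, 0.8 | constant 3% per day | about 14% | 6.95 to 7.03 (repeat runs) minus 3.68 = 3.27 to 3.35 days |
| 4 days, 0.8 | gamma, shape 2, mean 3 days, in 30% | 20% | 5.39 − 3.66 = 1.73 days |
| 4 days, 0.6 | gamma, shape 2, mean 2 days, in 22% | 18% | 0.58 days |

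Over these ranges the spurious difference in medians is about 0.5 to 3.3 days. It is smallest with early onset and uniform stays. Reducing log-SD to 0.4, outside the range, brings it to 0.27 days.

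**Other distributions, no true effect.** Complication rate 5%, 10% or 20%; Weibull onset with shape 0.3 (very early) to 1.0 (constant hazard); 2,000,000 patients per scenario. Differences in means:
- Coefficient of variation 0.5 (log-normal): +0.28 to +1.05 days at mean stay 4, and +0.44 to +1.58 days at mean stay 6.
- Coefficient of variation 1 (exponential): +1.22 to +4.01 days at mean stay 4, and +1.82 to +5.93 days at mean stay 6.

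The sign was positive in every scenario.

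**With a true effect of +4 days** (mean stay 5, coefficient of variation 0.5, 15% complicated):
- Very early onset: 4.36, an excess of 0.36 days (0.36/4 = 9%).
- Weibull shape 0.5: 4.63, an excess of 0.63 days (16%).
- Constant hazard: 5.30, an excess of 1.30 days (33%).

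**Not modelled.** In-hospital death, which can shorten stay among complicated patients.

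**The case against.** **The comparison is inferred.** No sentence says that total stay will be compared between patients with and without a complication. The ANOVA or Mann-Whitney sentence is generic and names neither stay nor objective 3, and a statistical analysis plan that is not shown may specify something else. This stands, so the point is conditional on that comparison being made. It does not dispose of the point, because the missing onset day is fixed in the protocol's own form and no later plan could fully make up for it on the core dataset.

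**The objective is descriptive.** It begins with describing, and the ethics section likens the study to a large audit. A reader might infer that the protocol intends to report extra stay as due to complications; it never says so. What remains is that the thing to be described is called an effect.

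**The size is soft.** This stands. A constant hazard with widely spread stay is the setting least favourable to the plan; early onset and uniform stays leave little bias. A reader might take several spurious days as established, but the documents contain nothing to support a particular figure.

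**Deaths work the other way.** This stands in part. A reader might infer that the net reported difference must be too large. Deaths among complicated patients may offset the bias, so that is not shown. They are a second distortion, though, and do not correct the first.

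**The remedy is heavy for a third secondary objective.** Onset days for conditions such as delirium or wound infection would be unverified, since the protocol plans no routine source data verification. That is a real cost, and the reason for offering a wording-only alternative.

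**Conclusion.** The point holds as a limitation built into the definitions and the form. If stay is compared between patients with and without a complication, days before onset enter the difference and longer stayers are over-represented in the exposed group. The direction of this component is firm: upward. Its size is not. About 0.5 to 3.3 days in medians under no true effect rests on the assumed log-normal stay and onset patterns, and narrower spread or earlier onset takes it lower. The sign of the net error, once deaths are included, was not established.

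The argument does not touch the primary incidence estimate or secondary objectives 1 and 2. The change is worth making because it is cheap before data collection and cannot be recovered from the core dataset afterwards.

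**What to change.** **Preferred.** Add one numeric box to the follow-up page for the day of first complication, with the day of surgery as day 0, in the format already used for critical care admission. Analyse objective 3 with the complication as a time-dependent exposure, by a landmark analysis or a multistate model with death as a competing event, and report extra days after onset.

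**Cost.** One more unverified field on a two-page form, and somewhat more analysis.

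**If the form cannot change.** Reword objective 3 to describe the association of complications with stay instead of their effect on it, and state that the difference includes stay before the complication. This costs wording only, but leaves the extra stay after onset unestimated.

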#### 5. METHODS

International, observational, 7-day cohort study. Each national group will select a single seven-day period for patient recruitment between April and June 2014.

**Inclusion Criteria:** All adult patients (aged ≥18 years) undergoing elective surgery in a participating hospital during the seven-day cohort period with a planned overnight stay.

**Exclusion Criteria:** Patients undergoing emergency surgery, planned day-case surgery or radiological procedures.

#### 6. STUDY PROCEDURES

#### **Consent procedures**

The requirement for patient consent will vary according to regulations in the participating nations. During the European Surgical Outcomes Study (EuSOS), which used identical methods of data capture, investigators were required to take written informed consent in only one of 28 nations. We anticipate that patient consent will not be required most nations taking part in ISOS on the basis that the dataset will only include variables documented as part of routine clinical care (see appendix) and that

ISOS protocol v1.0 Page 6 of 16

identifiable patient data will not leave the hospital where each individual patient is treated. Unless written informed patient consent is provided, only anonymised or coded data will be provided to the ISOS study group.

#### Country specific procedures for recruitment and patient consent

It is expected that worldwide, different countries have different regulatory requirements regarding patient consenting. Where required, the ISOS study protocol will include country specific appendices to describe specific procedures regarding the use of identifiable patient data and the procedures involved and regulatory approvals required. Where individual patient consent is given for participation, it is recognised that this may provide the opportunity to link ISOS data to national registry data on survival and other healthcare information. Plans for supplementary data collection in individual nations will also be detailed in a country specific appendix to this protocol.

#### Study data

Data will be collected on *all eligible patients* who undergo surgery during the study week. The proposed dataset is included in the appendix. Only routine clinical data will be included and where this is unavailable the domain will be left blank e.g. patients who do not require blood tests. It is possible that national groups may supplement their core data set with a very limited number of additional variables if these can be accommodated within the two page case record form (CRF) and they comply with regulations applied to this study.

#### **Data collection**

Data will be collected in individual hospitals on a paper CRF for each patient recruited. Paper CRFs will be stored within a locked office in each centre. This will include identifiable patient data in order to allow follow-up of clinical outcomes. Data will then be pseudo-anonymised by generating a unique numeric code and transcribed by local investigators onto an internet based electronic CRF. Each patient will only be identified on the electronic CRF by their numeric code. Thus the coordinating study team cannot trace data back to an individual patient without contact with the local team. A patient list will be used in each centre to match identifier codes in the database to individual patients in order to record clinical outcomes and supply any missing data points. Once the local co-ordinator confirms data entry is complete for their hospital they will receive a spreadsheet of raw (un-cleaned) data, allowing further checks for data completeness and accuracy.

ISOS protocol v1.0 Page 7 of 16

#### Study group organisation

ISOS will be led by the study management group who will be responsible for study administration, communication between project partners, data collation and data management. National co-ordinators will lead the project in each nation and:

- Identify local co-ordinators in participating hospitals
- Assist with translation of study paperwork as required
- Ensure distribution of study paperwork and other materials
- Ensure necessary regulatory approvals are in place prior to the start date
- Ensure good communication with the participating sites in his/her nation

Local co-ordinators in individual institutions will have the following responsibilities:

- Provide leadership for the study in their institution
- Ensure all relevant regulatory approvals are in place for their institution
- Ensure adequate training of all relevant staff prior to data collection
- Supervise daily data collection and assist with problem solving
- Act as guarantor for the integrity and quality of data collected
- Ensure timely completion of eCRFs by supervising local data entry
- Communicate with the relevant national co-ordinator

#### **End of Study Definition**

The end of the study is defined as the end of the 30-day follow-up for the last patient included. Data analysis shall follow this.

#### 7. STATISTICAL ANALYSIS

#### Sample size calculation

Our plan is to recruit as many centres as possible on an international basis and ask them to include all eligible patients in the study. A minimum of ten centres from any country will be required for participation and only centres including 20 valid patients will be included in the data analysis. We do not have a specific sample size and statistical models will be adapted to the event rate provided by the sample recruited.

ISOS protocol v1.0 Page 8 of 16

#### Statistical analysis

Hospitals including data describing less than 20 valid patients will be excluded in the data analysis. Data will be presented in the following geographical regions: Australasia, North America, Central & South America, Western Europe, Eastern Europe, Northern Europe, Southern Europe, Indian sub-continent, Middle East, China & South-East Asia, North Africa, Sub-Saharan Africa and Central Asia. No comparison will be made between individual nations and all national and institutional level data will be anonymised prior to publication. Categorical variables will be described as proportions and will be compared using chi-square or Fisher's exact test. Continuous variables will be described as mean and standard deviation, if normally distributed, or median and inter-quartile range, if not normally distributed. Comparisons of continuous variables will be performed using one-way ANOVA or Mann-Whitney test as appropriate. Univariate analysis will be performed to test factors associated with post-operative complications, admission to critical care and in-hospital death. Single-level and hierarchical multi-level logistic regression models will be constructed to identify factors independently associated with these outcomes and to adjust for differences in confounding factors. Factors will be entered into the models based on their univariate relation to outcome (p<0.05), biological plausibility and low rate of missing data. A stepwise approach will be used to enter new terms. Results of logistic regression will be reported as adjusted odds ratios (OR) with 95% confidence intervals. The models will be assessed through the use of sensitivity analyses to explore possible interacting factors and examine any effect on the results. A single final analysis is planned at the end of the study.

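### Single-level models and independent-observation tests stand beside the multi-level models with no stated priority, so inference on factors that differ mainly between hospitals can be anti-conservative

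*Protocol*

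**What the plan says.** Under Statistical analysis (section 7), the protocol plans two kinds of regression for complications, critical care admission and in-hospital death: "Single-level and hierarchical multi-level logistic regression models will be constructed to identify factors independently associated with these outcomes". The synopsis repeats this. Neither place says which kind is the main one. Adjusted odds ratios with 95% confidence intervals are promised for logistic regression in general, so for both kinds.

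For univariate work the same section says: "Categorical variables will be described as proportions and will be compared using chi-square or Fisher's exact test". Continuous variables get one-way ANOVA or Mann-Whitney. No allowance for clustering is named for any of these tests. Model entry depends on three things: a univariate p below 0.05, plausibility, and how complete the variable is.

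The sampling is by hospital. Each participating hospital is asked for every eligible patient in one week. The Sample size calculation section adds that "A minimum of ten centres from any country will be required for participation", and the analysis section that "Hospitals including data describing less than 20 valid patients will be excluded in the data analysis". The Introduction reports that survival after complications differs between hospitals and that mortality may differ between nations.

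The primary objective is descriptive: "To confirm the incidence of 30-day in-hospital complications following elective inpatient surgery". The outcome is "In-hospital post-operative complications of any cause (censored at 30 days following surgery"). No confidence interval or interval method is given for this proportion.

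**The concern.** Chi-square, Fisher, ANOVA, Mann-Whitney and single-level logistic regression all take patients as independent. Patients of one hospital share staff, practice and case mix, and the protocol's own background and its multi-level models both accept that outcomes differ between hospitals.

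Two consequences follow if the section is carried out as written. First, two sets of adjusted odds ratios for the same outcomes can disagree, and nothing fixes in advance which one is believed. Second, a factor that belongs to the hospital rather than the patient can look associated with outcome because a few hospitals have high or low rates. Region is constant within a hospital by construction. Use of a surgical checklist, recorded on the case record form, is plausibly set largely by hospital. The same p-values also help to decide which covariates reach the multi-level models.

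**Working it through.** **No figure to reproduce.** The protocol gives no power, ICC or interval width, and says "We do not have a specific sample size and statistical models will be adapted to the event rate provided by the sample recruited". The check therefore asks how far a test that ignores clustering departs from its nominal 5%.

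**Inputs.**
- From the protocol: at least m = 20 patients per analysed hospital. For a given ICC this is the most favourable case the plan allows.
- Assumed: ICC 0.02, 0.05 and 0.10; m = 50 as a larger hospital; equal hospital sizes. For the simulation: 200 hospitals, event rate 15%, 4,000 runs, beta-binomial hospital rates, Pearson chi-square.

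**Formulas.** Design effect DE = 1 + (m − 1) × ICC. For a factor constant within hospitals, the real size of a nominal 5% test is 2 × [1 − Φ(1.96/√DE)].

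**Worked case, m = 20, ICC 0.05.** DE = 1 + 19 × 0.05 = 1.95 and √DE = 1.40. Then 1.96/1.40 = 1.40, and the real size is about 16%.

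**Results.** The last three columns are simulated rejection rates for a null factor: one constant within hospitals, one recorded per patient whose prevalence varies between hospitals (ICC of the factor 0.10), and one balanced within hospitals.

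| m | ICC | DE | Size by formula | Hospital-level | Varies between hospitals | Balanced within |
|---|---|---|---|---|---|---|
| 20 | 0.02 | 1.38 | 9.5% | 10.1% | 5.5% | 5.0% |
| 20 | 0.05 | 1.95 | 16.0% | 16.5% | 6.0% | 4.6% |
| 20 | 0.10 | 2.90 | 25.0% | 24.6% | 7.2% | 4.8% |
| 50 | 0.02 | 1.98 | 16.4% | 17.5% | 5.9% | 5.2% |
| 50 | 0.05 | 3.45 | 29.1% | 28.3% | 8.5% | 4.6% |
| 50 | 0.10 | 5.90 | 42.0% | 41.3% | 11.2% | 4.6% |

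Formula and simulation agree. At 5% and 4,000 runs the simulation standard error is √(0.05 × 0.95/4000) = 0.34 points, so the last column is consistent with no inflation.

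**Limits of the check.** It is unadjusted. A single-level model with one binary factor behaves like the chi-square test. Case-mix adjustment may lower the residual ICC and so the inflation. Variation between nations is not included; for a factor such as region it would add to the problem.

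**Primary incidence, only if a simple binomial interval were used.** Its coverage is 2 × Φ(1.96/√DE) − 1, which is 84% at m = 20 and ICC 0.05. For 200 hospitals of 20 at 15%, the simple half-width is 1.96 × √(0.15 × 0.85/4000) = 1.1 points. Multiplied by 1.40 it becomes 1.5 points.

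**The case against.** The best defence is that the plan already contains the remedy. Hierarchical models cover all three binary outcomes, so a reader who infers that clustering is ignored throughout would be wrong. Which model leads, and which levels it has, could be set in a statistical analysis plan that is not shown. That answers part of the point. It does not answer the rest: the ordinary tests and the single-level models are named choices in the protocol, and a later plan would have to override them.

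Three stronger readings are tempting, and the text does not support them.
- **That the primary incidence is reported with too narrow an interval.** The protocol states no interval for it, and describing a variable as a proportion says nothing about its precision. The 84% above is conditional. The absolute change is also small for an objective with no threshold attached.
- **That p-values are too small across the board.** The case record form holds mainly patient-level factors such as age, comorbidity and blood results. Those balanced within hospitals keep the 5% size. Those of uneven prevalence showed 5.5% to 11.2% in the cases tabulated.
- **That screening hangs on these p-values.** The p-value is one of three criteria. A factor wrongly let in is only a candidate, and is then examined in adjusted models, including multi-level ones.

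It is also fair that regions are named only for presentation and that comparison of nations is ruled out. Regional differences matter here only if they are tested or modelled.

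**Conclusion.** The point stands in limited form. Section 7 gives models that ignore clustering equal standing with models that respect it, and prescribes independent-observation tests for univariate inference and for part of the screening. For factors constant within hospitals, a nominal 5% test has a real size of about 10% to 25% at 20 patients per hospital and about 18% to 41% at 50. The excess is modest for patient factors of uneven prevalence and absent for those balanced within hospitals.

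The direction follows from the design. The sizes rest on assumed ICCs, and only the 20 patients per hospital comes from the protocol. This should be fixed before the single final analysis. It does not undermine the primary objective.

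**What to change.** In section 7, and to match in the synopsis:

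1. State that all inference rests on the multi-level model, with patients within hospitals within nations.
2. Label the single-level models and the chi-square, Fisher, ANOVA and Mann-Whitney comparisons as descriptive.
3. Screen candidate factors with random-intercept univariable models, and keep the other two entry criteria as they are.
4. If a 95% interval is given for the primary incidence, allow for clustering by hospital. A hospital-clustered variance is the simplest way. The intercept of a random-intercept logistic model gives the risk in a typical hospital and would have to be averaged over hospitals to give the incidence.

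The cost is some wording, a little more computing, and wider intervals where hospitals differ. No new data are needed and nothing changes for patients.
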